13.2 Study Records Retention

Study documents will be retained for the longer of 3 years after close-out or 5 years after final reporting/publication of results.

13.3 Protocol Deviations

Protocol deviations will be reported to the NYUGSoM IRB per their guidelines. [name] is responsible for adhering to the IRB requirements.

13.4 Publication and Data Sharing Policy

The study will be registered on Clinicaltrials.gov prior to initiation. The steering committee ([name]) will oversee publications and presentations at meetings.

13.5 Study Finances

13.6 Funding Source

Funding for the study will be from the Doris Duke Charitable Foundation, Max Schlapp Fund, associated with the New York Community Trust, and from [name] departmental research fund. No data and no identifying information will be shared with these funders.

13.7 Costs to the Participant

Participants will incur no costs and transportation will be reimbursed.

13.8 Participant Reimbursements or Payments

Consistent with our other studies involving individuals with schizophrenia, we will compensate participants for their time and pay for their transportation costs. We will pay the following:

Screening Visit (approx. 2 hours): \$50

MRI Visit (20 minute MRI scan): \$50

Intervention Visit 1 (3 hours): \$150

Follow-up Visit 1 (20 minutes): \$25

Intervention Visit 2 (3 hours): \$150

Follow-up Visit 2 (20 minutes): \$25

Follow-up Visit 3 (20 minutes): \$50

If PLIFUS effects on fMRI and symptom ratings are not detected in the first 12 completers with good quality imaging data, the subsequent 4 participants will receive 3 sessions over 5 days. Participants will be paid \$50 for each of these additional sonifications.

14 Study Administration


17 Attachments

These documents are relevant to the protocol, but they are not considered part of the protocol. They are stored and modified separately. As such, modifications to these documents do not require protocol amendments.

- Device Manual attached

18 Schedule of Events

Activity	Screening Visit [Day -30 to -1]	MRI Visit [Day -30 to -1]	Intervention 1 [Day 0]	Intervention 2 [Day 7, 6-8]	Follow-up [Day 14, 13 to 15]
Study team procedures					
Consent	X				
Medical History	X				
Physical Exam	X				
Vital Signs	X				
Psychiatric History	X				
Psychiatric diagnosis (SCID)	X				
Demographics	X				
BPRS	X				X
PSYRATS			X	X	
BPAQ	X				
AHRS			X	X	
MoCA	X		X	X	
DESA			X	X	

CGI	X		X	X	
Experimental intervention					
Randomization		X			
PLIFUS or sham			X	X	
Safety Assessments					
SAFTEE & addendum			X	X	X
C-SSRS	X		X	X	X
Medical/psychiatric assessment			X	X	X
Imaging Assessments					
Structural MRI		X	X (pre and post-sonication)	X (pre and post-sonication)	
Resting state fMRI			X (pre and post-sonication)	X (pre and post-sonication)

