5.1 Inclusion Criteria

1. Males and females 18 to 55 years of age, inclusive, at time of informed consent
2. Must report current psychosis, as defined by a score of ≥ 4 on at least one of the following psychosis items on the Brief Psychiatric Rating Scale (BPRS): suspiciousness, hallucinations, unusual thought content, or grandiosity. Psychosis has to have persisted continuously for at least 4 weeks.
3. Must have a diagnosis of either schizophrenia or schizoaffective disorder as established by a Structured Clinical Interview for DSM-V (SCID)
4. If taking antipsychotic medication, the dose must be unchanged for at least 4 weeks prior to randomization. If not taking antipsychotic medication, must be intending not to start medication until after completion of the study (approximately 3 weeks)—this decision must be judged to be appropriate by the research psychiatrist and by the participant's clinician.
5. If assigned female at birth and of childbearing potential, patients must
 - a. have a negative urine pregnancy test (all participants assigned female at birth regardless of childbearing potential will be required to submit a pregnancy test), and
 - b. not be nursing or planning a pregnancy for the duration of the study through 30 days after the last sonication visit, and
 - c. be abstinent or willing to use a reliable method of birth control from the Screening Visit and continue with the same method until termination from the study.

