5.2 Exclusion Criteria

1. Current substance abuse / dependence for substances other than nicotine and THC, (i.e. alcohol, amphetamines, barbiturates, etc.)
 - a. A positive urine toxicology screen (excluding THC, tricyclic antidepressants, or benzodiazepines (if prescribed)).
 - b. Moderate or severe cannabis use disorder.
2. Diagnosis of major mood disorder or other Axis I disorder other than schizophrenia or schizoaffective disorder as determined by a SCID
3. Current or recent suicidal ideation – suicidal ideation with intent or plan (indicated by affirmative answers to items 4 or 5 of the Suicidal Ideation section of the baseline C-SSRS) in the 6 months prior to screening or have a history of suicide attempt in the past 6 months or subjects who represent a significant risk of suicide in the opinion of the investigator.
4. Subjects who represent a significant risk of violence determined by the assessing clinician or PI, based on history, presentation, and the Buss-Perry Aggression Questionnaire ⁴⁸ or a rating of ≥ 5 on the BPRS hostility item.
5. Pregnant or nursing or positive urine pregnancy test.
6. Significant medical or neurological illness by history or physical exam, including seizure disorder, history of loss of consciousness lasting more than 30 minutes related to head trauma or intellectual developmental disorder.
7. Metal implants, such as a cardiac pacemaker, intra-cardiac lines, neurostimulator, medication infusion device, jewelry/piercings that cannot be removed, and/or any other metal in the body that cannot be removed.
8. Claustrophobia
9. A history of brain surgery
10. History of syncopal episode within the past 6 months
11. Cochlear implants
12. Skin disease at intended stimulation sites
13. The consumption of more than four alcoholic units within 24 hours before Intervention Visit 1 and 2, and any recreational drugs within 48 hours before Intervention 1 and 2

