5.7 Total Number of Participants and Sites

The study will be performed at a single site (NYU Langone Manhattan) and participants will be enrolled in order to achieve 12 completers who complete both sonication/sham sessions. Potentially, 4 additional participants will be enrolled if a single session of PLIFUS does not reduce functional connectivity or symptoms in the first 12 completers with good quality imaging data compared to sham, to assess whether 3 sessions of PLIFUS administered over 5 days reduces functional connectivity and symptoms.

Screening and follow-up assessments can be performed at the Psychiatry Research Center at [name] or NYUGSoM Research Imaging Center at [name] MRIs and sonication/sham will always be performed at the NYUGSoM Research Imaging Center at [name] Participants will be recruited at NYU Langone Manhattan, NYU Langone Brooklyn, and Bellevue Hospital.

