5.8 Participant Withdrawal or Termination

5.8.1 Reasons for Withdrawal or Termination

Participants are free to withdraw from participation in the study at any time upon request. An investigator may terminate participation in the study if:

- Any clinical Adverse Event (AE), or other medical condition or situation occurs such that continued participation in the study would not be in the best interest of the participant
- The participant meets an exclusion criterion (either newly developed or not previously recognized) that precludes further study participation

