5.8.2 Handling of Participant Withdrawals or Termination

If participants withdraw or are terminated before completion of the study, we will attempt to conduct the safety assessments at 24-48 hours and 7 days if the participant experienced one session.

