7.2.3 MRI Visit (Days -30 to -1)

- Obtain structural MRI scan for neuronavigation

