7.2.4 Intervention Visits

Intervention Visit 1: (Day 0)

- Administer CGI, C-SSRS, SAFTEE, SAFTEE addendum, and PSYRATS
- Obtain structural MRI scan for fMRI registration (5 minutes)
- Obtain fMRI resting state scan (20 minutes)
- Administer AHRS and DESA prior to starting intervention
- Administer PLIFUS/sham over 10 minutes (re-administer AHRS and DESA at 5 minutes)
- Repeat AHRS and DESA immediately after PLIFUS/sham
- Obtain structural MRI scan for fMRI registration (5 minutes)
- Obtain fMRI resting state scan (20 minutes)
- AHRS and DESA repeated immediately after fMRI scan
- PSYRATS and CGI 60 minutes after PLIFUS/sham
- Psychiatric and medical assessment, including MoCA, SAFTEE, and SAFTEE addendum, 1 hour after PLIFUS/sham

Intervention Visit 1B: (Day 1-2) (may be remote)*

- AHRS and DESA
- SAFTEE & addendum
- C-SSRS

Intervention Visit 2 (Day 6-8)

- Administer CGI, C-SSRS, SAFTEE, SAFTEE addendum, and PSYRATS
- Obtain structural MRI scan for fMRI registration (5 minutes)
- Obtain fMRI resting state scan (20 minutes)
- Administer AHRS and DESA prior to starting intervention
- Administer PLIFUS/sham over 10 minutes (re-administer AHRS and DESA at 5 minutes)
- Repeat AHRS and DESA immediately after PLIFUS/sham
- Obtain structural MRI scan for fMRI registration (5 minutes)
- Obtain fMRI resting state scan (20 minutes)
- AHRS and DESA repeated immediately after fMRI scan
- PSYRATS and CGI 60 minutes after PLIFUS/sham
- Psychiatric and medical assessment, including MoCA, SAFTEE, and SAFTEE addendum, 1 hour after PLIFUS/sham

Intervention Visit 2B (Day 7-9) (may be remote)*:

- AHRS and DESA
- SAFTEE & addendum
- C-SSRS

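### Randomization is scheduled at the MRI Visit, before the Day 0 exclusion check and baseline scan, although nothing needs the allocation until the first session is set up

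*Combined protocol and SAP*

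**What the plan says.** In Section 18 the Randomization row has a single mark, under "MRI Visit [Day -30 to -1". The body text gives no other assignment point. Section 7.2.3 lists one procedure for that visit, "Obtain structural MRI scan for neuronavigation", and Section 4.1 says only that the schedule will be made in Matlab. Ratio, blocking, list length and the handling of replacements are not given. The Protocol Summary describes the active session as counterbalanced with sham.

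These steps come after the MRI Visit:

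- Exclusion 13 (Section 5.2): "The consumption of more than four alcoholic units within 24 hours before Intervention Visit 1 and 2", together with recreational drugs in the preceding 48 hours. For Visit 1 this can be judged only on Day 0.
- Termination under Section 5.8.1: "The participant meets an exclusion criterion (either newly developed or not previously recognized) that precludes further study participation".
- The baseline functional scan on Day 0, before PLIFUS or sham (Section 7.2.4): "Obtain fMRI resting state scan (20 minutes".

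On replacement, Section 5.7 says "participants will be enrolled in order to achieve 12 completers who complete both sonication/sham sessions", and the Protocol Summary continues enrollment until there are 12 completers with good quality imaging. The primary analysis (Section 9) is in completers, using a mixed model with baseline, treatment, sequence and a random participant effect; no period term is named. Inclusion 4 (Section 5.1) requires, for those on antipsychotics, that "the dose must be unchanged for at least 4 weeks prior to randomization".

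**The concern.** Assigning session order before the last eligibility check lets people be lost between randomization and treatment. Here the early assignment brings nothing in return. The neuronavigation MRI, the pre-session ratings and the pre-session fMRI are the same under either order, and the condition matters only when the operator sets up sonication or sham.

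Two things are at stake. First, if the list is balanced, a person lost before Day 0 uses up an order slot and the replacement takes the next one, so the orders actually started can drift from 6:6. Section 9.1.1 itself names an order effect as the main worry about imbalance. Second, because Inclusion 4 is anchored to randomization, the stability requirement as worded stops at the MRI Visit and does not cover the interval up to the baseline scan. No other section extends it.

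**Working it through.** The sample size of 12 rests on goals and budget (Section 9, Sample Size). There is no power calculation, dropout rate or list specification to reproduce, so the loss rates and list types below are assumptions.

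**Length of the interval.** The visit window allows up to 30 days. Section 5.6 expects the whole process to take at most 21 days, and Section 7.2.5 puts the final visit on Day 14-16. That leaves 21 − 16 = 5 to 21 − 14 = 7 days before Day 0. Thirty days is therefore the permitted limit, and about a week is what the plan expects.

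**Number randomized.** With loss rate L before Day 0, the expected number randomized to start 12 is 12/(1 − L): 12/0.9 = 13.3, 12/0.8 = 15.0, 12/0.7 = 17.1.

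**Order split among 12 starters.** For blocked lists, 20,000 trials were simulated per setting, with independent loss and each replacement taking the next slot. For simple 1:1 randomization the binomial is exact: P(8:4 or worse) = 2 × (495 + 220 + 66 + 12 + 1)/4096 = 1588/4096 = 0.388.

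| List (assumed) | Loss before Day 0 | P(6:6) | P(7:5 or worse) | P(8:4 or worse) |
|---|---|---|---|---|
| Blocks of 4 | 0% | 1.00 | 0 | 0 |
| Blocks of 4 | 10% | 0.62 | 0.38 | 0.03 |
| Blocks of 4 | 20% | 0.47 | 0.53 | 0.07 |
| Blocks of 4 | 30% | 0.40 | 0.61 | 0.13 |
| Block of 12 | 10% | 0.60 | 0.40 | 0.04 |
| Block of 12 | 20% | 0.44 | 0.57 | 0.11 |
| Block of 12 | 30% | 0.36 | 0.64 | 0.17 |
| Simple | any | 0.23 | 0.77 | 0.39 |

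The 0% row is what Day 0 assignment gives for starters under a blocked list. The last row shows that timing is irrelevant under simple randomization.

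**What a split costs.** Let n1 and n2 be the numbers in each order. The active-minus-sham difference carries the visit difference with a plus sign in one order and a minus sign in the other. Without a period term, the share left in the mean is (n1 − n2)/12: 2/12 = 0.17 at 7:5 and 4/12 = 0.33 at 8:4. A sequence main effect does not remove this. If the visits differed by 0.5 SD (assumed), an 8:4 split would leave about 0.5 × 0.33 = 0.17 SD in the contrast, against the plan's threshold of 0.5. With a period term the residual goes, and only efficiency is lost: 4·n1·n2/144 = 140/144 = 0.97 at 7:5 and 128/144 = 0.89 at 8:4.

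**The case against.** The strongest reply is that the drift in order depends on a list the plan does not describe. Counterbalanced suggests equal orders but does not establish blocking. That stands, and so do two further limits. The figures describe 12 starters, whereas the analysis uses completers with good imaging; Visit 2 dropout and unusable scans can unbalance that set whenever randomization occurs. And a period term would remove the residual visit effect at any split.

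A reader might also infer more than the documents support:

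- *That people lost before Day 0 are not followed.* Section 5.8.2 does say "we will attempt to conduct the safety assessments at 24-48 hours and 7 days if the participant experienced one session", but those are post-session checks. Section 7.2.6 lists assessments for anyone who withdraws early, with no condition that a session occurred, and Section 7.12 records events from consent onward.
- *That results by randomized participant become impossible to report.* Section 13.1 drops early terminators from the electronic database only; data are collected on paper forms, and Section 13.2 retains study documents. The gap between randomized and analysed sets comes mainly from the completer analysis, the replacement rule and the retention rule, all of which remain under Day 0 randomization.
- *That the Day 0 scan itself removes people.* Section 7.2.4 describes a scan and states no quality gate. Nor do the documents say whether someone who fails exclusion 13 on the day is dropped or rebooked.
- *That the treatment comparison is biased.* Participants and raters are blind to order, and loss before any treatment does not by itself bias a within-person contrast.

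**Conclusion.** The point holds in a limited form. Section 18 places randomization ahead of a Day 0 exclusion check and the baseline scan with no offsetting benefit, and people lost in between are replaced. The effect on order balance arises only if the list is blocked or otherwise balanced. With blocks of 4 and assumed pre-Day-0 loss of 10%, 20% or 30%, the starters reach 8:4 or worse about 3%, 7% or 13% of the time; under simple randomization the timing contributes nothing. The 0.17 SD figure needs an 8:4 split, an assumed 0.5 SD visit difference and a model without period, so it illustrates a possible size and is not an expected one. The mismatch with Inclusion 4 needs none of these assumptions: as scheduled, the stability period ends before the baseline scan. The priority is modest for an exploratory pilot, but the correction is nearly free.

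**What to change.** Move the Randomization mark in Section 18 from the MRI Visit to Intervention 1 [Day 0]. Add to Sections 4.1 and 9.1.1 that the unblinded operator opens the next allocation once the Day 0 eligibility recheck, pre-session ratings and pre-session fMRI are complete, and before sonication or sham begins. The same text should name the list type and say how a replacement is allocated, since the size of the problem turns on both.

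The change is one table cell and a short addition, with no extra visit or staff, because the operator already sets up the condition that day. The one real cost is that the reference date in Inclusion 4 moves to Day 0, so medication stability has to be rechecked then. Loss after Day 0 is untouched by this change. The 30-day window in Section 18 and the 21-day maximum in Section 5.6 should be reconciled in the same revision.
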